#### 9.3.2 Outcome Assessment

##### Primary outcome

The most proximal Hb value within 4 weeks preceding (and including) the date of first ESA administration will be used to define the Hb level at index. The proportion of patients with the Hb value at index  $\leq 10\text{g/dL}$  (as per SmPC), and  $\leq 11\text{ g/dL}$  (as per Study 20070782) is the primary outcome.

There is no pre-specified threshold for determining an acceptable minimal clinical difference between Study 20080782 and this study. The results will be contextualized against Study 20070782 and other literature on ESA use.

##### Secondary outcome

For Hb levels during treatment, all available measurements during ESA treatment will be collected per patient.

Hb values achieved at pre-specified time points during treatment (ie, 3 weeks, 4 weeks, 6 weeks, and 9 weeks) will be reported. These time points are in line with recommended dosing intervals of the SmPC and Study 20070782.

The baseline demographic and clinical characteristics of patients initiating treatment with an ESA and receiving myelosuppressive chemotherapy will be described as the number and proportion (%) for each of the covariates listed in Section 9.3.3.

The duration of prescription will be collected for each ESA prescription. The mean duration of prescription will be described, and the number and proportion (%) of patients with an ESA prescription at 3, 4, 6, and 9 weeks will be described.

### 9.3.3 Covariate Assessment

- Demographics
  - Age, assessed at index as categorical in 5-year age bands: 18-20, 21-25, 26-30, 31-35, 36-40, 41-45, 46-50, 51-55, 56-60, 61-65, 66-70, 71-75, 76-80, 81-85, > 85
  - Sex
  - Country
- Clinical characteristics at index
  - Type of currently treated malignancy
  - Year of diagnosis for currently treated malignancy
  - Disease stage at diagnosis (nonmetastatic and metastatic)
  - Eastern Cooperative Oncology Group (ECOG) status
- Chemotherapy
  - Timing of administration
  - Drug(s) regimen
- Comorbidities
  - Hypertension
  - Acute liver disease
  - Chronic liver disease
  - Epilepsy
  - Sickle cell anaemia
  - Diabetes (1 and 2)
  - Thromboembolic events
  - Cardiac disease
  - Chronic pulmonary disease
  - Cerebrovascular disease
  - Peripheral vascular disease
  - Red cell aplasia
  - Chronic inflammatory disease (eg, rheumatoid arthritis, inflammatory bowel disease)
  - HIV or AIDS
  - Hepatitis B or C
- RBC transfusions
  - Count of RBC transfusions and number of units at baseline (in the last 3 months before index date)
  - Count of RBC transfusions during treatment

### 9.3.4 Validity and Reliability

The data collected for this study will be recorded in electronic case report forms (eCRFs) from routine clinical practice for the documentation and decision-making for a patient's care. Due to this, it is expected that the data collected will be routinely available in the medical records as the data include treatment(s) and evaluations involved in standard medical practice. By its nature, medical chart review is open to inter-observer variability in interpretation and abstraction of medical records. In addition, not all outcomes may appear in the charts. The problems of medical chart review are well recognized and various strategies have been proposed to increase validity and reliability of the data.

The eCRF will be structured in a way that allows sites to specifically indicate when requested data are missing or unknown. Sites participating in the study will be fully trained, in data entry and use of the study-specific data base and eCRFs. In addition, a number of quality control checks will be conducted at different time points on the collected data as described in Sections 9.6 and 9.8.

### 9.4 Data Sources

Source data will include patient medical records and charts (both electronic and/or paper based) as well as pathology and pharmacy databases. Study site staff will enter data into the eCRF retrospectively for each patient following enrolment into the study, based on data collected from routine clinical visits. Data for each patient will be recorded in accordance with normal clinical practice and no additional assessments or tests considered as interventional will be required.

### 9.5 Study Size

The planned sample size is estimated at 1625 patients who received an ESA during myelosuppressive chemotherapy, and at an estimated **24** study sites across the **6** countries. Recruitment will be competitive, with no limit on the number of **sites activated per country, or** patients recruited per site, country, or year, however patient recruitment will be reviewed regularly to minimise recruitment bias. Characteristics of recruited patients will regularly be compared, where data allows, against non-recruited site data, or published regional, and national data. Comparisons will include the distribution of cancer diagnoses and sociodemographic characteristics. The number of patients approached compared to the number consented per site will be regularly reviewed. The distribution of recruitment within and between countries will also be regularly reviewed. Where discrepancies arise, assertive outreach to site and country investigators will aim to encourage widened recruitment and site selection. Previous

European prospective studies describing Hb levels in patients receiving darbepoetin alfa and other ESAs enrolled between 150 and 1,800 patients (Aerts et al, 2012, Smakal et al, 2018, Berbec et al, 2018). In an analysis of patients with solid tumours who received darbepoetin alfa in European clinical practice between 2008 and 2010, darbepoetin alfa was initiated at a Hb level < 10 g/dL in 50% of breast cancer, 57% of CRC, 60% of ovarian, and 57% of lung cancer patients (Aerts et al, 2012). The Hb level at ESA initiation was between 9 and < 11 g/dL in 80% of breast cancer, 76% of CRC, 76% of ovarian, and 77% of lung cancer patients. A study in multiple European countries to evaluate quality of life in CIA patients treated with ESAs between 2011 and 2013 found that baseline Hb was ≤ 10 g/dL in 97% of patients (clinicaltrials.gov a). A study of darbepoetin alfa use for CIA in Central and Eastern Europe between 2012 and 2016 found that 73% had Hb < 10 g/dL at baseline (Smakal, 2018). A study of darbepoetin alfa use for CIA in Romania between 2011 and 2015 found that 81% had Hb between 9 and 11 g/dL at baseline (Berbec et al, 2018).

The table below provides estimates for the half-width of the 95% CI surrounding a range of proportions (columns) and sample size (rows) expected. One half the width of the 95% CI for proportions is calculated using an exact method proposed by Clopper and Pearson (Clopper and Pearson, 1934). The sample size is expected to provide adequate precision for estimation of the primary objective, but not for comparisons between initiation groups.

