## **9.7 Data Analysis**

### **9.7.1 Planned Analyses**

#### **9.7.1.1 Interim Analysis**

**An interim analysis will be conducted by the CRO (IQVIA) when the study reaches 600 participants. The aim of the interim analysis is to describe the study population, report interim findings on the primary outcomes, the proportion of patients with Hb values at index  $\leq 10$ g/dL (as per SmPC), and  $\leq 11$  g/dL (as per Study 20070782), and to determine the probability that the results found in the interim analysis would be different if conducted with a larger sample size. The results of the interim analysis will be valuable in examining the prescribing practices at various index Hb values currently observed in Study 20190404 and comparing those with results from similar studies (eg, Study 20170210) to assist with future interpretation and assessment of results from Study 20190404. The interim analysis sample size of 600 has been selected as it provides a similar level of precision in the highest predicted proportion of patients with Hb  $\leq 10$  g/dL (at a 0.9 proportion), as would the aimed 1625 patient sample at the lowest predicted proportion of patients with Hb  $\leq 10$  g/dL (at a 0.5 proportion, [Table 1](#)).**

All variables will be presented as stated in the primary analysis (see Section 9.7.2). Categorical variables will be presented as counts and percentages of the total. Continuous variables will be described using the mean, standard deviation, median, first quartile, third quartile, minimum and maximum. Point estimates will be accompanied by 95% CIs. No imputation method will be used for missing data. Patients with missing age, sex, information about malignancy diagnosis, ESA treatment (start date), chemotherapy treatment, and Hb value recorded at baseline will be excluded during the selection procedure (see Section 9.2.3). For the other variables, missingness will be quantified and reported as the number and percentage of missing observations for each variable. Patient demographics and clinical characteristics will be presented overall. The primary outcomes, the proportion of patients with Hb values at index  $\leq 10$ g/dL (as per SmPC), and  $\leq 11$  g/dL (as per Study 20070782), will be presented overall. No subgroup analyses will be reported in the interim analysis.

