#### **9.9.1.3 Selection Bias**

The biggest threat to validity is the potential selection bias, through the selection of study sites and the recruitment of patients.

The selection of study sites will not be completely at random; research-focused study sites, those with capacity to conduct the data collection, and those that are likely to

prescribe the product according to the guidelines are more likely to respond, and therefore a degree of selection bias is unavoidable.

Patients if mandated by local legislation, are required to give informed consent for their data to be collected. The proposed study is a retrospective chart review and selection bias may be introduced during the consenting procedure. Patients who are not contactable to give informed consent may differ from those who are contactable in terms of time of treatment (those who were treated earlier in the included study period may be more difficult to contact), demographic characteristics, and treatment outcome. Bias may also be introduced through the process of informed consent, whereby those willing to give informed consent may be systematically different from those who do not due to treatment outcome (either dissatisfaction with care or due to death).

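### The stated precision in 9.5 and the n = 600 interim rationale treat patients from about 24 sites as independent, so they are more favourable than the design supports

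*Protocol*

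**What the plan says.** Protocol 9.5 (Study Size) states: "The planned sample size is estimated at 1625 patients who received an ESA during myelosuppressive chemotherapy". It expects to find these patients "at an estimated 24 study sites across the 6 countries". Accrual is uncapped: "Recruitment will be competitive, with no limit on the number of" active centres in a country or of patients at any one centre. The safeguard offered is a regular review of accrual for recruitment bias.

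On precision, the same section says: "One half the width of the 95% CI for proportions is calculated using an exact method proposed by Clopper and Pearson". Table 1 gives the resulting half-widths for n from 40 to 1800 and proportions from 0.5 to 0.9. The conclusion drawn is: "The sample size is expected to provide adequate precision for estimation of the primary objective".

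Section 9.7.1.1 (Interim Analysis) takes its sample size from that table: "The interim analysis sample size of 600 has been selected as it provides a similar level of precision in the highest predicted proportion", namely 0.9, as the full 1625 patients would give at the lowest predicted proportion, 0.5.

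The analysis text (9.7.1.1, 9.7.2.1) promises 95% confidence intervals without naming a method. The protocol nowhere mentions an ICC, a design effect or between-site variance. The regular review of recruitment in 9.5 and the text in 9.9.1.3 deal with bias, not variance.

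**The concern.** The Clopper-Pearson interval is exact for independent patients. Here about 68 patients per site (1625/24) share prescribers and local ESA policy, and the primary outcome is the haemoglobin level at which those prescribers start treatment. A positive ICC is therefore plausible, and any positive ICC makes the true uncertainty larger than Table 1 shows. Uncapped competitive recruitment allows very unequal sites, which adds to it.

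The primary result is a proportion with its confidence interval, set beside the label and Study 20070782. Precision stated too favourably would make label-consistent or trial-consistent use look more firmly established than it is. The interim analysis is also meant to say how likely the result is to differ with a larger sample, and that depends partly on how much sites vary.

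The interim rationale has a second weakness that needs no clustering argument. It matches a half-width at one proportion with a half-width at another, so it does not show how much precision is given up at 600 patients.

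**Working it through.** **Inputs from the protocol.** n = 1625 and about 24 sites (9.5); interim n = 600 (9.7.1.1); 95% Clopper-Pearson (9.5).

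**Assumed inputs, not in the protocol.** Site ICC from 0.005 to 0.10; equal sites unless stated; all 24 sites active at both time points.

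**Step 1: reproduce the plan's figures.** With x = np,

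half-width = [Beta(0.975; x + 1, n − x) − Beta(0.025; x, n − x + 1)] / 2.

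All 105 cells of Table 1 reproduce to within 5 × 10⁻⁷, for example 0.024793 (n = 1600, p = 0.5) and 0.024831 (n = 600, p = 0.9). For n = 1625, which is not a row of the table, the formula gives 0.0246 at p = 0.5 and 0.0149 at p = 0.9. The table is correct under independence.

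**Step 2: add a design effect.** DE = 1 + (m − 1) × ICC with m = 1625/24 = 67.7; effective n = 1625/DE; then the Step 1 formula at the effective n. For ICC 0.02: DE = 1 + 66.7 × 0.02 = 2.33, effective n = 696, half-width 0.0378.

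The last column is the approximate coverage of an unadjusted nominal 95% interval, 2Φ(1.96/√DE) − 1.

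| ICC (assumed) | DE | Effective n | Half-width, p = 0.5 | Ratio to 0.0246 | Coverage |
|---|---|---|---|---|---|
| 0.005 | 1.33 | 1219 | 0.0285 | 1.16 | 91% |
| 0.01 | 1.67 | 975 | 0.0319 | 1.30 | 87% |
| 0.02 | 2.33 | 696 | 0.0378 | 1.54 | 80% |
| 0.05 | 4.34 | 375 | 0.0518 | 2.10 | 65% |
| 0.10 | 7.67 | 212 | 0.0693 | 2.82 | 52% |

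(The first half-width is 0.02845 before rounding, hence 2.8 points.) A beta-binomial simulation of the exact interval at p = 0.7 (100,000 studies, sites of 67 or 68 patients) gave coverage of 92%, 88%, 81%, 66% and 53%, in line with the approximation.

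**Step 3: vary the sites.**
- Unequal sites: DE = 1 + (m(1 + CV²) − 1) × ICC, where CV is the coefficient of variation of site size. With CV = 1 (assumed), ICC 0.01 gives DE 2.34 and half-width 0.0379; ICC 0.05 gives DE 7.72 and 0.0695.
- More sites: with 60 equal sites (illustrative), m = 27.1. At ICC 0.02, DE = 1.52 and the half-width is 0.0304, against 0.0378 with 24 sites.

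**Step 4: the interim rationale.**
- As written, under independence: 0.0248 (n = 600, p = 0.9) against 0.0246 (n = 1625, p = 0.5). It reproduces.
- At the same proportion, still under independence: 0.0408 against 0.0246 at p = 0.5, a ratio of 1.66; 0.0248 against 0.0149 at p = 0.9, about the same ratio.
- With clustering the stated match fails. For n = 600, m = 25. At ICC 0.02 the figures are 0.0304 (n = 600, p = 0.9) against 0.0378 (n = 1625, p = 0.5); at ICC 0.05 they are 0.0374 against 0.0518.
- At ICC 0.05 the effective n is 600/2.20 = 273 at the interim and 375 at 1625, if the same 24 sites supply all patients.

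**The case against.** The strongest reply is that this concerns planning text only. Clopper-Pearson is named for study size, not for the analysis; 9.7 leaves the interval method open, and a statistical analysis plan could adjust for site. That stands. A reader might infer that the reported intervals will be too narrow, but the protocol supports this only if the one method it names is carried forward.

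Four further limits also stand.

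- **Size.** A reader might conclude that the intervals are about half as wide as they should be. That holds only near an assumed ICC of 0.05 with equal sites. At 0.01 the unadjusted interval has about 77% of the proper width (1/√1.67), and the protocol gives no ICC.
- **Number of sites.** It is tempting to say that further patients add little because the sites are fixed. They are not: 9.2.2 and 9.5 allow more sites, and 9.9 describes a pool of 195 potential sites.
- **Evidence of between-site variation.** Section 9.9.1.3 says that sites likely to "prescribe the product according to the guidelines are more likely to respond, and therefore a degree of selection bias is unavoidable". This contrasts sites that respond with sites that do not. It does not say that participating sites differ in adherence, and selective response could make them more alike. The case for a positive ICC rests on the nature of the outcome.
- **Consequence.** This is an estimation study with no hypothesis, no pre-specified threshold (9.3.2), no numerical precision target and no interim stopping rule. Even at ICC 0.05 the half-width is about 5 points, small beside the 50% to 97% that 9.5 cites from earlier studies for cut-offs around 10 g/dL. Selection bias, which 9.9.1.3 calls the main threat, is not addressed by a wider interval.

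On the interim, 9.7.1.1 says openly that it compares the highest predicted proportion with the lowest. Nothing is concealed, but the comparison still does not show what precision 600 patients give relative to 1625.

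**Conclusion.** The point holds for the planned precision in 9.5 and the interim rationale in 9.7.1.1. Both rest on an independence assumption that a multi-centre sample with a prescriber-driven outcome is unlikely to meet. Table 1 contains no arithmetic error.

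The direction follows from any positive ICC. The size depends on the assumed ICC, on how unequal the sites are and on how many are opened: 1.16 to 2.82 times the stated half-width for ICC 0.005 to 0.10 with 24 equal sites. Clustering by country is not included. Under-coverage of the reported intervals is conditional on an unadjusted method being used in the analysis. The 1.66-fold difference between n = 600 and n = 1625 at a common proportion needs no ICC assumption.

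This should be fixed. It is not critical, because no threshold, error rate or stopping rule depends on it.

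**What to change.** 1. In 9.5, restate the half-widths for about 24 sites with a design effect over a stated ICC range, allowing for unequal site sizes, and reword the adequacy sentence to match. Update the figures if more sites are opened.
2. In 9.7, state that the confidence intervals for the primary proportions and mean haemoglobin take site as the cluster, for example a cluster-robust variance with a t reference on (sites − 1) degrees of freedom. Report the site ICC at the interim.
3. In 9.7.1.1, replace the n = 600 rationale with half-widths for 600 and 1625 patients at the same proportion, and base any predictive probability on a model that includes between-site variation.

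The cost is a change of wording and a standard procedure. The abstraction form described in 9.6 already records recruitment by centre, so no new data and no extra patients are needed. The drawback is that the stated precision becomes less favourable.

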**Table 1. Half Width of the 95% CI for Various Estimated Proportions of (eg, Hb ≤ 10 g/dL), by Sample Size (n)**

Sample size	Proportion				
	0.5	0.6	0.7	0.8	0.9
40	0.161982	0.159041	0.149845	0.132978	0.104356
60	0.131938	0.129486	0.121816	0.10773	0.083733
80	0.113952	0.111807	0.105093	0.092755	0.071697
100	0.101679	0.099748	0.093704	0.082594	0.063609
200	0.071342	0.069959	0.06563	0.057666	0.044027
300	0.058002	0.056869	0.053319	0.046787	0.035591
400	0.050092	0.049108	0.046028	0.040357	0.030636
500	0.044714	0.043833	0.041074	0.035996	0.027287
600	0.040756	0.039951	0.037431	0.032790	0.024831
700	0.037687	0.036942	0.034606	0.030307	0.022933

800	0.035218	0.034520	0.032335	0.028312	0.021410
900	0.033176	0.032518	0.030457	0.026662	0.020152
1000	0.031451	0.030826	0.028870	0.025269	0.019091
1100	0.029968	0.029373	0.027507	0.024073	0.018181
1200	0.028677	0.028106	0.02632	0.023031	0.017389
1300	0.027538	0.02699	0.025274	0.022113	0.016691
1400	0.026525	0.025997	0.024342	0.021297	0.01607
1500	0.025615	0.025105	0.023507	0.020564	0.015514
1600	0.024793	0.024299	0.022751	0.019901	0.015011
1700	0.024045	0.023565	0.022063	0.019299	0.014554
1800	0.02336	0.022894	0.021435	0.018747	0.014136

## 9.6 Data Management

All data will be collected by site investigators identified by the **Clinical Research Organisation (CRO ([IQVIA])**). Data are abstracted by site staff from source data into an electronic database. Protocol-specific training and eCRF completion instructions will be provided to all site staff delegated to abstract patient data.

Each patient will be assigned a unique identification number at the time of the first data entry. This unique identification number will be used to link data to subsequent retrospective data entries. The data will be abstracted by site staff from patient's medical records using an electronic abstraction form that will provide an integrated, transparent tool to facilitate and record centre recruitment, case identification, patient selection, and study progress at the centre and patient level. The electronic database will include eCRFs designed to capture the variables and outcomes of interest. The data collected for this study will be derived from medical records that are kept per routine clinical practice for the documentation and decision-making for a patient's care.

### 9.6.1 Obtaining Data Files

Data capture for this study is planned to be electronic:

- All source documentation supporting entries into the eCRFs must be maintained and available upon request.
- Updates to eCRFs will be automatically documented through the software's "audit trail."
- To ensure the quality of clinical data across all patients and sites, automated logic checks related to data entry will be implemented. In addition, clinical data management review will be performed on patient data received. During this review, patient data is checked for consistency, omissions, and any apparent discrepancies. To resolve any questions arising from the clinical data management review process,

data queries and/or site notifications are created in the electronic database for site resolution and closed by the reviewer.

- The physician signs only the Physician Verification Form for this EDC study. This signature indicates that the physician inspected or reviewed the data on the eCRF, the data queries, and site notifications, and agrees with the content.

Protocol-specific training on the eCRFs will be provided to all study site abstractors in advance of the study data collection period to ensure clarity on the questions and the data to be captured are accurate.

### **9.6.2 Linking Data Files**

Not applicable.

### **9.6.3 Review and Verification of Data Quality**

The clinical monitor or designee is responsible for verifying the eCRFs at regular intervals throughout the study to verify adherence to the protocol completeness, accuracy, and consistency of the data, and adherence to local regulations on the conduct of research. The clinical monitor or designee is to have access to patient medical records and other study-related records needed to verify the entries on the eCRFs where allowed, in accordance with the local laws and regulations.

## **9.7 Data Analysis**

### **9.7.1 Planned Analyses**

#### **9.7.1.1 Interim Analysis**

**An interim analysis will be conducted by the CRO (IQVIA) when the study reaches 600 participants. The aim of the interim analysis is to describe the study population, report interim findings on the primary outcomes, the proportion of patients with Hb values at index  $\leq 10$ g/dL (as per SmPC), and  $\leq 11$  g/dL (as per Study 20070782), and to determine the probability that the results found in the interim analysis would be different if conducted with a larger sample size. The results of the interim analysis will be valuable in examining the prescribing practices at various index Hb values currently observed in Study 20190404 and comparing those with results from similar studies (eg, Study 20170210) to assist with future interpretation and assessment of results from Study 20190404. The interim analysis sample size of 600 has been selected as it provides a similar level of precision in the highest predicted proportion of patients with Hb  $\leq 10$  g/dL (at a 0.9 proportion), as would the aimed 1625 patient sample at the lowest predicted proportion of patients with Hb  $\leq 10$  g/dL (at a 0.5 proportion, [Table 1](#)).**

All variables will be presented as stated in the primary analysis (see Section 9.7.2). Categorical variables will be presented as counts and percentages of the total. Continuous variables will be described using the mean, standard deviation, median, first quartile, third quartile, minimum and maximum. Point estimates will be accompanied by 95% CIs. No imputation method will be used for missing data. Patients with missing age, sex, information about malignancy diagnosis, ESA treatment (start date), chemotherapy treatment, and Hb value recorded at baseline will be excluded during the selection procedure (see Section 9.2.3). For the other variables, missingness will be quantified and reported as the number and percentage of missing observations for each variable. Patient demographics and clinical characteristics will be presented overall. The primary outcomes, the proportion of patients with Hb values at index  $\leq 10$ g/dL (as per SmPC), and  $\leq 11$  g/dL (as per Study 20070782), will be presented overall. No subgroup analyses will be reported in the interim analysis.

In addition, Bayesian posterior probabilities and predicted probabilities may be calculated to describe the distribution of proportion of patients with a Hb value at index  $\leq 10$ g/dL and the probability of that proportion being above a given threshold.

